12.3. Endpoints and Derivations

12.3.1. Sensitivity, Specificity, PPV, and NPV

Table 7 will be used to classify the combined pelvic lymph node packets (left or right) from Cohort A and biopsy from Cohort B according to its ¹⁸F-DCFPyL image result (positive or negative) generated from central imaging review and its histopathology result (positive or negative for prostate cancer) generated by the sites' pathology review. Nodes identified on ¹⁸F-DCFPyL PET/CT images in areas that were not removed in surgery for Cohort A will not be tabulated due to absence of histopathology.

Table 7: Classification of ¹⁸F-DCFPyL Imaging Result and Histopathology Result for Cohorts A and B Separately

	Histopatho	ology Result	
¹⁸ F-DCFPyL Image	Positive*	Negative	
Positive	ТР	FP	I(p)
Negative	FN	TN	I(n)
	R(p)	R(n)	Nı

TP=true positive; FP=false positive; FN=false negative; TN=true negative.

R(p) and R(n) denote the subjects with a positive or negative lobe or biopsy, respectively, based on histopathology. I(p) and I(n) denote the subjects with a positive and negative lesion, respectively, based on the ¹⁸F-DCFPyL image. N_1 indicates the number of subjects with evaluable pelvic lymph node packets from Cohort A or the number of subjects with evaluable biopsies from Cohort B.

*Positive histopathology should be for prostate cancer only.

The following statistics will be computed:

- Sensitivity = TP/R(p),
- Specificity = TN/R(n),
- Positive predictive value (PPV) = TP/I(p),
- Negative predictive value (NPV) = TN/I(n).

For Cohort A, a true positive or true negative must be determined from imaging and histopathology aligning on outcome overall.

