### 5.5.7. Sensitivity, Specificity, PPV, and NPV

Sensitivity, specificity, PPV and NPV will be defined based on a F-DCFPyL image result (positive or negative) and a histopathology result (positive or negative).

Table 3: Classification of F-DCFPyL Imaging Result and Histopathology Result

	Histopatho		
 F-DCFPyL Image Positive* Negative			
Positive	TP	FP	I(p)
Negative	Negative FN		I(n)
	R(p)	R(n)	N

TP=true positive; FP=false positive; FN=false negative; TN=true negative.

The following statistics will be computed:

- Sensitivity = TP/R(p),
- Specificity = TN/R(n),
- Positive predictive value (PPV) = TP/I(p),
- Negative predictive value (NPV) = TN/I(n).

R(p) and R(n) denote the number of subjects with positive and negative histopathology results, respectively.

I(p) and I(n) denote the number of subjects with positive and negative F-DCFPyL images, respectively.

N indicates the number of subjects

\*positive histology should be for prostate cancer only

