### 5.5.7.1. Primary Endpoints and Pelvic Lymph Nodes

The primary endpoints of sensitivity and specificity are defined from lymph node imaging results and corresponding pelvic lymph node histology. For an imaging result to be deemed positive for this endpoint, the tissue must have first been removed from that corresponding area. This ensures that an imaging result has the ability to align with the results achieved from pathology. This will be applied to Cohort A subjects only.

PPV and NPV will also be calculated as secondary endpoints from the pelvic lymph nodes. The same definitions used below will apply.

Criteria for Positive PyL Imaging Result	Criteria for Lymph Node Dissection and Positive Histology
If Right or Left Pelvic Lymph Nodes Minimum Template = Positive and  • Tissue was removed from left template and total left nodes removed ≥1 and Template Left Pelvic LN Lesion Count	≥1 positive lymph node on right template if Template Right Pelvic LN Lesion Count from imaging is ≥0 or ≥1 positive lymph nodes on left template if Template Left Pelvic LN Lesion Count from
≥1 or  • Tissue was removed from right template and total right nodes removed ≥1 and Template Right Pelvic LN Lesion Count ≥1  or  Tissue was removed from Pre-sacral nodes and total pre-sacral nodes removed ≥1 and Pre-Sacral Pelvic LN Lesion Count ≥ 1	imaging is ≥0 or ≥1 positive lymph nodes on pre-sacral nodes if Pre-Sacral Pelvic LN Lesion Count from imaging is ≥0 or ≥1positive lymph nodes on other pelvic lymph nodes if Other Pelvic Lymph Node Count from imaging is ≥0
or Tissue was removed from Other lymph nodes and Total nodes removed >=1 and Other Pelvic LN Lesion Count ≥ 1 or	

If tissue was removed from right template and total right nodes removed ≥1 and resection included tissue along the external iliac artery and Right pelvic lymph node external iliac artery= positive or

If tissue was removed from left template and total left nodes removed ≥1 and resection included tissue along the external iliac artery and left pelvic lymph node external iliac artery= positive or

If tissue was removed from right template and total right nodes removed ≥1 and resection included tissue along the common iliac vein and Right pelvic lymph node common iliac vein= positive or

If tissue was removed from left template and total left nodes removed ≥1 and resection included tissue along the common iliac vein and left pelvic lymph node common iliac vein=positive or

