If tissue was removed from right template and total right nodes removed ≥1 and resection included tissue along the common iliac artery and Right pelvic lymph node common iliac artery= positive or

If tissue was removed from left template and total left nodes removed ≥1 and resection included tissue along the common iliac artery and left pelvic lymph node common iliac artery= positive

If Template Right Pelvic LN Lesion Count from imaging is  $\geq 0$  and Total number of positive lymph nodes from Right Template  $\geq 1$  or

If Template Left Pelvic LN Lesion Count from imaging is  $\geq 0$  and Total number of positive lymph nodes from Left Template  $\geq 1$ 

If any of the above criteria are met for imaging then PyL Imaging Result=Positive. If Cohort =A and lymphadenectomy was performed, and lesion counts from imaging results are available for at least one location (right, left, pre-sacral or other) but the above criteria are not met for imaging, then PyL Imaging Results = Negative.

If the above criteria for histology are met then Histology is positive. If all available positive lymph nodes=0 where the corresponding lesion count from imaging≥0 then Histology is negative.

If the lesion counts from all 4 locations (right, left, pre-sacral, and other lymph nodes) are not evaluable on imaging or tissue is not removed from all 4 locations then this endpoint will be missing.

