#### 5.5.7.3. Prostate Gland

Sensitivity, specificity, PPV and NPV will be calculated from imaging and histology results from the prostate gland. This will be performed for subjects in Cohort A only.

Criteria for Positive PyL Imaging Result	Criteria for Positive Histology
For category = PYL and Prostate gland right lesion count $\geq 1$ or Prostate gland left lesion count $\geq 1$	If Prostate gland right lesion count ≥0 from imaging and Adenocarcinoma is present at right side of prostate or
	Prostate gland left lesion count ≥0 from imaging and Adenocarcinoma is present at left side of prostate

If Cohort = A and Adenocarcinoma results are not missing for the right or left side of the prostate and the above criteria is not met, then result = Negative.

If imaging results are both not evaluable or the presence of adenocarcinoma is missing from both the left and right side of the prostate then this endpoint is missing.

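### SAP 5.5.7.1 lets the reader's image decide the truth standard: a subject with a pathology-positive node at a site that the reader could not evaluate can be scored histology-negative, and node status can differ between readers

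*SAP*

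**What the plan says.** SAP 5.5.7.1 sets out the histology side of the primary endpoint location by location. For the right template the positive criterion is "≥1 positive lymph node on right template if Template Right Pelvic LN Lesion Count from imaging is ≥0". The left, pre-sacral and other pelvic nodes have the same form, and the condition is repeated for the right and left templates later in the section. A count of zero or more means that the site was read, so a site without an evaluable count contributes no positive nodes.

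The negative criterion is "If all available positive lymph nodes=0 where the corresponding lesion count from imaging≥0 then Histology is negative".

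The section recognises that a count may be not evaluable. On the imaging side, the endpoint is missing only in this case: "If the lesion counts from all 4 locations (right, left, pre-sacral, and other lymph nodes) are not evaluable on imaging". One available location is enough for an imaging-negative result.

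Lesion counts are supplied by each reader (SAP 5.5.8), and sensitivity and specificity are computed per reader (SAP 7.6.1). PPV and NPV for the pelvic nodes follow the same rule: "The same definitions used below will apply".

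Elsewhere the truth standard depends on pathology alone. Protocol 12.3.1 takes the result from the sites' pathology review and adds: "R(p) and R(n) denote the subjects with a positive or negative lobe or biopsy, respectively, based on histopathology". The notes to SAP Table 3 say: "R(p) and R(n) denote the number of subjects with positive and negative histopathology results, respectively". Neither carries a condition on image readability. Both documents also blind the local pathologists to imaging (Protocol 8.4, SAP 4.1).

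**The concern.** A reference standard should not depend on the test it is used to judge. Under this rule it does, because the index-test reader decides which pathology findings count.

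The rule can move a subject with proven nodal metastasis out of R(p) and into R(n). That removes a potential miss from the sensitivity denominator and adds a node-positive subject to specificity, PPV and NPV. If the reader calls nothing positive at the resected sites, the subject becomes a true negative, which favours both co-primary endpoints. If the reader calls a resected site positive, the subject becomes a false positive. Under the protocol's subject-level rule ("For Cohort A, a true positive or true negative must be determined from imaging and histopathology aligning on outcome overall") that same subject would be a true positive.

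The three readers can also be tested against different truth standards, although success requires the same two readers on both endpoints. SAP section 10, which lists departures from the protocol, does not mention this one. The prostate-gland rule in SAP 5.5.7.3 uses the same construction: "Prostate gland left lesion count ≥0 from imaging and Adenocarcinoma is present at left side of prostate".

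**Working it through.** **Plan's own figure.** Inputs from SAP 4.3: two-sided 5%, 80% power, sensitivity 0.40 vs 0.60, specificity 0.80 vs 0.878, prevalence 20%, 10% non-evaluable. The SAP's formula gives:

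- Sensitivity: n = 47.09, and 47.09/0.20 = 235.5, so 236.
- Specificity: n = 184.5, and 184.5/0.80 = 230.6, so 231.
- The larger is 236, and 236/0.90 = 262.2, stated as 262.

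The sample size reproduces and is not in dispute. It implies about 236 × 0.20 = 47 node-positive and 189 node-negative subjects.

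**Rule logic.** The four-location lesion-count rules were coded (the vessel-level imaging criteria were left out) and applied to one fixed pathology report: both templates dissected, one positive node on the right, none on the left.

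| Reader's count, right | Reader's count, left | Histology under SAP | Cell |
|---|---|---|---|
| 0 | 0 | Positive | FN |
| 1 | 0 | Positive | TP |
| Not evaluable | 0 | Negative | TN |
| Not evaluable | 1 | Negative | FP |

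All four cells can be reached from the same pathology. The missing rule does not intervene, because it needs all four locations to be not evaluable.

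**Sensitivity.** The documents give no rate of partly unreadable pelves. Assume that a share u of the 47 node-positive subjects is moved, so k = 47u, and that SAP sensitivity among the rest is 0.60. Then TP = 0.60(47 − k). If no moved subject has a PET-positive resected site, pathology-based sensitivity is TP/47:

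- u = 2%: 27.64/47 = 0.588
- u = 5%: 26.79/47 = 0.570
- u = 10%: 25.38/47 = 0.540

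If 12.2% of the moved subjects do have one (1 − 0.878, the design false-positive rate), the value at u = 5% is (26.79 + 0.122 × 2.35)/47 = 0.576. If the moved subjects are made non-evaluable, it stays at 0.60.

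**Specificity under the SAP at u = 5%** (k = 2.35, TN = 0.878 × 189 = 165.94):

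- all moved subjects TN: (165.94 + 2.35)/191.35 = 0.8795
- all FP: 165.94/191.35 = 0.867
- 12.2% FP: 0.878

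**NPV at u = 5%**, 12.2% of moved subjects PET-positive: FN = 0.40 × 44.65 = 17.86 and 0.878k = 2.06.

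- SAP: (165.94 + 2.06)/(165.94 + 2.06 + 17.86) = 0.904
- Pathology-based: 165.94/(165.94 + 17.86 + 2.06) = 0.893

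**Decision for one reader.** Lower limit = p − 1.96√(p(1 − p)/n), to exceed 0.40:

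| TP/n | p | Lower limit | Result |
|---|---|---|---|
| 26/47 | 0.553 | 0.411 | pass |
| 25/47 | 0.532 | 0.389 | fail |
| 25/46 | 0.543 | 0.3995 | fail |
| 25/45 | 0.556 | 0.410 | pass |
| 24/45 | 0.533 | 0.388 | fail |

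Moving one miss changes no result here. Moving two reverses the result at 25 true positives but not at 24.

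**Chance of passing, one reader.** With the k moved subjects counted as misses under pathology-based truth and 0.60 sensitivity in the rest, exact binomial probabilities are 0.738 under both rules at k = 1. At k = 2 they are 0.778 under the SAP and 0.679 under pathology-based truth.

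**The case against.** The strongest defence is region matching. SAP 5.5.7.1 wants image and pathology to be comparable site by site, and Protocol 12.3.1 already drops PET-positive nodes from areas that were not resected. On that view, an unread site should drop out on both sides. This argues for setting the subject to missing for that reader, or for analysing by region. It does not justify calling a node-positive subject histology-negative in a subject-level analysis. The protocol's restriction also runs the other way: it discards imaging findings that lack pathology, not pathology findings that lack imaging.

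The missing rule might be read as making the endpoint missing whenever any of the four locations is unread. The same section contradicts that reading, since one available location is enough for an imaging-negative result.

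The points about size stand. The frequency is unknown. If every site is always read, the condition is only a non-missing check and has no effect. Harm needs one site unreadable, another readable, and every positive node at an unreadable site. One moved subject reverses no decision in the example, and at the design value (28/47, lower limit 0.455) the reader passes anyway. The loss of sensitivity appears only if an unread diseased site counts as a miss. That convention is debatable, as is crediting a true positive for a PET finding away from the known disease. These points limit the likely effect. They do not make the rule correct.

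**Conclusion.** The concern holds, and the rule must be fixed. As written, proven nodal metastasis can be entered as disease-free in a confirmatory analysis, with node status varying by reader, contrary to Protocol 12.3.1 and the SAP's own Table 3 notes. That conclusion rests on the text and needs no assumed rate.

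The numerical effect does rest on assumptions. For 2% to 10% of node-positive subjects moved, sensitivity is overstated by 0.012 to 0.060 (0.60 against 0.588 to 0.540) when unread diseased sites count as misses, and by nothing when those subjects are made non-evaluable. Specificity shifts only slightly, in either direction. The test against 0.40 is sensitive to this because it rests on about 47 subjects per reader, and two reclassified misses can turn a marginal fail into a pass.

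**What to change.** Replace the histology rule in SAP 5.5.7.1 with wording such as:

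> Histology is positive if at least one removed pelvic lymph node, from any location, is positive for prostate cancer, and negative if nodes were removed and all are negative. This status is derived once per subject from pathology and used for all readers, whether or not the location was evaluable on imaging.

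The existing imaging rule then decides the cell. A node-positive subject whose positive site is unread is FN if no resected site is PET-positive and TP if one is, never TN or FP.

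Add to SAP 7.6.2 a sensitivity analysis that treats such subjects as non-evaluable for that reader. This shows how far the result depends on the convention. Make the same correction to the prostate-gland rule in 5.5.7.3.

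Optionally, and as a separate matter, keep the protocol's subject-level outcome as primary and add a supportive location-matched sensitivity. A TP would then need at least one location that is both PET-positive and histology-positive, with the iliac sub-sites mapped to their side. This would show how many true positives come from an off-site PET finding.

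The cost is SAP wording and a few lines of programming before database lock. Pathology and imaging are already recorded by location, so no new data are needed. The price is a little more analysis work and possibly a slightly lower sensitivity and NPV.

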10.5. Biopsy and Surgical Pathology

Immediately following biopsy or surgery, the specimens will be sent for histopathological processing and analysis at the site in accordance with the study Pathology Manual.

Gross handling of the prostate gland and lymphadenectomy specimens, if applicable, will include whole gland assessment and sectioning of the entire prostate gland, overall measurement of specimen size, lesion location, dissection and description (including location) of identified lymph nodes, and submission of lymph nodes in their entirety plus all remaining fibroadipose tissue for each harvested regional packet. Histopathology results of the prostate gland and pelvic lymph nodes (Cohort A) or biopsy location (Cohort B) will be recorded in the eCRF.

Should a Cohort A subject forego RP surgery and undergo alternative procedure for prostate cancer (e.g., biopsy), the procedure and corresponding histopathology data will be recorded in the eCRF. Likewise, should a Cohort B subject receive additional procedure for prostate cancer, the procedure and corresponding histopathology data will be recorded in the eCRF.

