#### **5.4.3.** Evaluable Set

*Evaluable subjects* in Cohort A are those who were dosed, had a prostatectomy or lymphadenectomy, and provided a F-DCFPyL PET image result (positive or negative) and a corresponding histopathology result (positive or negative).

Evaluable subjects in Cohort B are those who were dosed, received a conventional image guided biopsy, and provided a F-DCFPyL PET image result (positive or negative) and a corresponding histopathology result (positive for prostate cancer or negative), along with a conventional image that confirms the location of the histopathology sample.

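### SAP 5.5.7.1 sets no minimum node count for negative histology, so a dissection that yields no nodes can be scored as a true negative whatever the scan shows

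*SAP*

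**What the plan says.** Four rules in the SAP decide how a Cohort A subject is classified on the primary endpoint.

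- **Positive imaging (5.5.7.1).** Each route needs nodes as well as tissue. For the left template the condition is "Tissue was removed from left template and total left nodes removed ≥1", plus a lesion count of at least 1. The right template, pre-sacral and iliac-vessel routes carry the same kind of condition, and so does the route for other pelvic nodes: "Tissue was removed from Other lymph nodes and Total nodes removed >=1 and Other Pelvic LN Lesion Count ≥ 1".
- **Negative imaging (5.5.7.1).** This is the default. If a lymphadenectomy was done and a lesion count exists for at least one location, "but the above criteria are not met for imaging, then PyL Imaging Results = Negative".
- **Negative histology (5.5.7.1).** "If all available positive lymph nodes=0 where the corresponding lesion count from imaging≥0 then Histology is negative". Nothing is said about how many nodes were examined.
- **Missing endpoint (5.5.7.1).** The endpoint is missing if the lesion counts are not evaluable, or if "tissue is not removed from all 4 locations then this endpoint will be missing".

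The Evaluable Set (SAP 5.4.3) takes Cohort A subjects who were dosed, "had a prostatectomy or lymphadenectomy, and provided a" positive or negative scan result with matching histopathology. It does not mention nodes. Protocol 10.5 describes the pathology submission as "submission of lymph nodes in their entirety plus all remaining fibroadipose tissue for each harvested regional packet", so a packet holds more than identified nodes.

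**The concern.** The plan treats removed tissue and removed nodes as separate conditions, because the positive-imaging rules ask for both. Tissue without nodes is therefore a state the plan foresees. The node condition was written on one side only: it stops a scan from being positive, but it does not stop histology from being negative. A subject in whom no node was examined offers no node-level truth, yet can enter both the numerator and the denominator of specificity as a success.

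Specificity is the gatekeeping co-primary endpoint, since sensitivity is tested only after specificity succeeds (SAP 7.6.1). NPV for the pelvic nodes uses the same definitions. The bias runs in one direction, in favour of the product.

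**Working it through.** **1. The plan's own sample size.** SAP 4.3 gives n = {[z(α/2)·√(P0(1−P0)) + z(β)·√(P1(1−P1))]/(P1−P0)}², with two-sided α of 0.05, 80% power and 20% prevalence of positive histopathology.

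- Sensitivity, 0.40 against 0.60: n = 47.09; 47.09/0.20 = 235.5, so 236.
- Specificity, 0.80 against 0.878: n = 184.48; 184.48/0.80 = 230.6, so 231.
- The larger is 236, and 236/0.9 = 262.2. The stated 236 evaluable and 262 dosed reproduce.
- Expected histology-negative subjects: 0.80 × 236 = 188.8, so R(n) = 189.

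**2. Tracing one subject.** Suppose tissue was removed, pathology found no node at any location, and the positive-node counts are recorded as 0.

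| Step | Rule in SAP 5.5.7.1 | Result |
|---|---|---|
| Imaging positive? | Template, pre-sacral, other-node and iliac routes need at least 1 node removed; the two closing template rules need at least 1 positive node | Cannot be met |
| Imaging default | Lymphadenectomy done, at least one lesion count available | Negative, even if the reader counted lesions |
| Histology | Available positive-node counts are 0 | Negative |
| Missing? | Tests evaluable lesion counts and tissue removed | Not triggered by absent nodes |

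Negative imaging with negative histology is a true negative. The subject adds 1 to TN and 1 to R(n) in TN/R(n), and 1 to TN and 1 to I(n) in NPV. He never enters R(p), so sensitivity does not move.

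**3. Size for one reader.** Let k be the number of such subjects among the 189. The documents give no rate, so k is assumed to be 0 to 9, or about 0% to 5% (9/189 = 4.8%).

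Success needs the lower limit of the normal-approximation 95% interval to exceed 0.80:
- 161/189 = 0.8519; 0.8519 − 1.96·√(0.8519 × 0.1481/189) = 0.801, which passes.
- 160/189 = 0.8466; the same formula gives 0.795, which fails.

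The threshold is therefore 161. With k automatic true negatives kept in, the reader needs 161 − k correct among 189 − k. Apparent specificity is [(189 − k)·Sp + k]/189, a gain of k(1 − Sp)/189. The chance of passing is the exact binomial tail at Sp = 0.80:

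| k | Gain in specificity (points) | Needed among subjects with nodes | Chance of passing, kept in | Chance of passing, set to missing |
|---|---|---|---|---|
| 0 | 0 | 161/189 | 4.2% | 4.2% |
| 2 | 0.21 | 159/187 | 4.8% | 3.2% |
| 4 | 0.42 | 157/185 | 5.6% | 3.7% |
| 9 | 0.95 | 152/180 | 7.8% | 3.5% |

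The last column moves unevenly because the threshold is a whole number. At a true specificity of 0.878 the gain is 0.13 to 0.58 points for k = 2 to 9.

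**4. Trial level.** If readers were independent on the remaining subjects, the chance that at least two of three pass is 3p² − 2p³: 0.5% at k = 0 (p = 4.2%), 0.9% at k = 4 (p = 5.6%) and 1.7% at k = 9 (p = 7.8%). Correlation between readers would raise these figures.

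**The case against.** **Other text points towards exclusion.** SAP 5.4.3 asks for a histopathology result that matches the scan, SAP 5.5.7.1 derives the endpoint from pelvic-node histology, and Protocol 12.3.1 counts subjects with evaluable node packets. A study team could use any of these to drop a node-free case. None of them states a node minimum, however, and the explicit rule in 5.5.7.1 is met by a count of 0.

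**A clean packet may count as a negative result.** The protocol classifies combined packets and submits all the fatty tissue with them, so a fully examined packet without cancer is arguably negative. That is a fair position, but it does not explain why the same packet disqualifies a positive scan.

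**The case may be rare.** It needs no nodes at right, left, pre-sacral and other sites together, in subjects scheduled for prostatectomy with pelvic node dissection. This stands, and it limits the size of the problem.

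Some stronger readings go beyond the documents:

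- *A node-free dissection is always a true negative.* This depends on 0 being recorded. If the field is blank, the histology rule is either met vacuously or undefined, and the SAP does not say which. The missing-data wording also has two readings: tissue absent from every location, or from any one. The second would drop many more subjects, but both test tissue rather than nodes.
- *Every reader gains.* A reader without an evaluable lesion count at any location has a missing endpoint.
- *The histology rule alone is at fault.* Without the node condition on imaging, a node-free subject with a positive scan would be a false positive. The two rules act together.
- *The two-of-three requirement gives no protection.* Readers still differ on all other subjects, the trial-level rate is lower than the per-reader rate, and overall success also needs sensitivity. It is true only that evaluable readers gain these true negatives together.

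**Conclusion.** The gap is real on the text, but conditional and probably small. Where no node is found and 0 is entered, the rules give a true negative for each reader with an evaluable lesion count, whatever the scan shows. Where the entry is blank, the outcome is unsettled.

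For an assumed 2 to 9 such subjects among 189, specificity rises by 0.2 to 1.0 points at a true value of 0.80, and the per-reader chance of passing rises from 4.2% to between 4.8% and 7.8%. The 4.2% starting point already exceeds the nominal one-sided 2.5%; that comes from the normal-approximation interval, not from this rule. A reader might infer much larger inflation by assuming that a tenth of dissections are node-free, but nothing in the documents supports such a share.

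The point still merits correction, because it sits in a primary-endpoint derivation and can act only in the product's favour.

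**What to change.** In SAP 5.5.7.1, require at least one node examined (total nodes removed ≥1) in at least one location with an evaluable lesion count before histology can be negative. Otherwise set the pelvic-node endpoint to missing, whether the positive-node field holds 0 or is blank. Report the number of such subjects and list them in Listing 16.2.6-1. If SAP 5.4.3 is also amended to remove them from the Evaluable Set, list them in Listing 16.2.3-1, which covers only excluded subjects.

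The node counts are already needed for the imaging rule, so no new data are required. The cost is a few uninformative subjects lost from the specificity denominator. At a true specificity of 0.878, exact per-reader power is 88.5% with 189 subjects, and 85.2%, 86.5% or 84.9% when 2, 4 or 9 are set to missing, all above the planned 80%.

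The clause works at subject level. It does not change the coding of a subject with a node-free side and negative nodes elsewhere, which depends on the imaging rule.

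### The closing rule in SAP 5.5.7.1 can be read as requiring tissue from all four nodal locations, so the denominators of both co-primary endpoints are not fixed

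*SAP*

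**What the plan says.** SAP Section 5.5.7.1 builds one PET result and one histology result per Cohort A subject from four nodal locations: right template, left template, pre-sacral and other pelvic nodes.

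- **PET positive.** The criteria are specific to a location and joined by *or*. For a positive location, "the tissue must have first been removed from that corresponding area".
- **PET negative.** This applies when lymphadenectomy was done, "lesion counts from imaging results are available for at least one location", and no positive criterion is met.
- **Histology positive.** At least one positive node at any location whose PET lesion count is zero or more.
- **Histology negative.** "If all available positive lymph nodes=0 where the corresponding lesion count" from imaging is zero or more.
- **Missing.** The section closes with a rule in two halves: if the lesion counts from all four locations cannot be evaluated, or "tissue is not removed from all 4 locations then this endpoint will be missing".

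Three other places bear on the last rule. For the prostate gland, SAP Section 5.5.7.3 makes the endpoint missing when PET is not evaluable on both sides or "the presence of adenocarcinoma is missing from both the left and right side of the prostate". SAP Section 5.4.3 counts dosed Cohort A subjects as evaluable if they "had a prostatectomy or lymphadenectomy, and provided a" PET result and a corresponding histology result. SAP Section 10 describes the same set as needing both operations. Neither statement sets a number of nodal locations. Protocol Section 12.3.1 classifies the combined left or right node packets and does not require pre-sacral or other nodes.

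**The concern.** The tissue half of the closing rule has two readings. On the stricter one, a subject is missing unless tissue came from every one of the four locations. On the other, a subject is missing only if tissue came from none of them. *Other* is a residual category, so under the stricter reading a man could leave the primary analysis simply because the surgeon took nothing beyond the two templates.

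The rule decides who enters the denominators of both co-primary endpoints, and SAP Section 5.6.1 allows no imputation. Two competent programmers could therefore obtain different primary results from the same data. SAP Section 2 sends changes to populations or endpoints through an amendment, but a reading chosen during programming would not be recorded there. If the choice were made after results were visible, it would be open to the charge of being driven by the data.

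**Working it through.** **1. The plan's own figure.** Inputs, from SAP Section 4.3: sensitivity 0.40 against 0.60, specificity 0.80 against 0.878, two-sided alpha 0.05, power 80%, prevalence of positive histology 20%, 10% drop-out or non-evaluable. The SAP's formula is n = {[z(α/2)·√(P0(1−P0)) + z(β)·√(P1(1−P1))] / (P1−P0)}².

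- Sensitivity: n = 47.09 node-positive; 47.09/0.20 = 235.5, rounded up to 236.
- Specificity: n = 184.48 node-negative; 184.48/0.80 = 230.6.
- The larger is 236; 236/0.90 = 262.2. The stated 236 evaluable and 262 dosed both reproduce.

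**2. One subject under each rule.** Take a man with right and left templates dissected, no pre-sacral or other nodes removed, and PET counts evaluable throughout.

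| Rule | Outcome |
|---|---|
| PET criteria, SAP 5.5.7.1 | positive or negative |
| Histology criteria, SAP 5.5.7.1 | positive or negative |
| Evaluable set, SAP 5.4.3 | included |
| Left or right packets, protocol 12.3.1 | classified |
| Closing rule, tissue from none of the four | not missing |
| Closing rule, tissue from every one of the four | missing |

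Only the last line conflicts with the others.

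**3. Size under the stricter reading.** Let f be the share of otherwise evaluable subjects with tissue from all four locations. Protocol Section 10.3 records the extent of dissection but gives no distribution, so every f below is an assumption. Also assumed: 20% prevalence in those who remain. Inverting the SAP formula, power = Φ{[(P1−P0)·√n − z(α/2)·√(P0(1−P0))] / √(P1(1−P1))}, with n = 236·f·0.20 for sensitivity and 236·f·0.80 for specificity.

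| f | Subjects | Node-positive | Node-negative | Power, sensitivity | Power, specificity |
|---|---|---|---|---|---|
| 1.00 | 236 | 47.2 | 188.8 | 80.1% | 81.0% |
| 0.90 | 212 | 42.5 | 169.9 | 75.8% | 76.2% |
| 0.75 | 177 | 35.4 | 141.6 | 68.0% | 67.0% |
| 0.50 | 118 | 23.6 | 94.4 | 50.9% | 46.8% |
| 0.25 | 59 | 11.8 | 47.2 | 28.9% | 22.4% |

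These are per reader and per endpoint; they leave out the requirement that the same two of three readers succeed on both. In the last row, 11.8 × (1 − 0.60) = 4.7, which is below the SAP Section 7.2.1 threshold of 5, so that sensitivity figure is rough. Keeping 236 analysable subjects would need 236/(0.90·f) dosed: 292 at f = 0.90 and 525 at f = 0.50, against 262 planned. Under the none-of-four reading, the first row stands unchanged.

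**4. A subject with no matched location.** Now suppose tissue from none of the four is meant, and take a man with an evaluable PET count on the left only and tissue from the right only. He is not missing, since one count and one tissue site exist. PET is negative, because one location has a count and no positive criterion can be met. Histology cannot be positive, because the right side has no corresponding count. The histology-negative rule then has no location to act on. It is either undefined or satisfied by an empty set. In the second case, even a positive right node would leave him counted as a true negative.

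**The case against.** The best defence is that the sentence has only one sensible meaning. Its first half speaks of lesion counts at all four locations not being evaluable, and the rule that a count at one location is enough for PET negative forces that half to mean that none is evaluable. The tissue half has the same form. The prostate-gland rule uses the same logic, and the *or* structure and the word *available* would lose their purpose if all four sites were compulsory. This is persuasive as to intent. It does not settle the text: the prostate-gland rule shows that the intended logic can be written plainly, and here it was not.

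Two stronger inferences should be resisted.

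- A reader might take the at-least-one-location rule as a direct contradiction of the tissue clause. That rule concerns PET counts once lymphadenectomy has been done and says nothing about how many sites need tissue. The conflict lies in the outcome for the same subject, and only under the stricter reading.
- A reader might infer that the none-of-four reading freely admits subjects whose PET and histology do not overlap. It does not. PET positive needs tissue from the same area, both histology rules need a corresponding PET count, and SAP Section 5.4.3 asks for a corresponding histology result. What survives is the corner case in step 4 of the working.

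**Conclusion.** The point holds as a drafting ambiguity in the definition of the primary endpoint. The probable intent is that the endpoint is missing when tissue came from none of the four locations, but neither document states this.

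If the probable reading is programmed, nothing is lost: 236 evaluable subjects, with per-reader power of about 80% for sensitivity and 81% for specificity. If the stricter reading is programmed, the loss depends on f. Even at f = 0.90, both tests fall below the planned 80%.

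The documents do not show that the plan intends the exclusion, or that the trial would be left with almost no power. A reader might reach the latter by supposing that few men have all four sites sampled. Nothing in the documents places f that low, and even at f between 0.10 and 0.30 the formula gives sensitivity power of about 14% to 34%: inadequate, but not nil. The unmatched-location gap is secondary, and the documents give no basis for estimating how often it would arise.

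**What to change.** Replace the closing sentence of SAP Section 5.5.7.1 with: *The endpoint is missing unless at least one of the four locations has both an evaluable PET lesion count and removed tissue.* State that the PET-negative and histology-negative rules apply only to those matched locations. This removes the double reading and closes the unmatched-location gap.

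The cost is one sentence, one matching condition, a SAP amendment and a programming check, all before database lock. No procedure, data item or sample size changes. The extent of dissection is already in the eCRF, so the number of subjects affected by each reading can be counted without looking at PET results or node status.
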